#### 1.2.6 Rationale for benefit-risk ratio

A previous study has shown that that the functionality of stents with novel side-holes is the same as that of standard stents in terms of safety. The novel stent does not result in increased risk of irritation, inflammation and hydronephrosis [18]. Furthermore, SEM/EDX imaging showed that the novel design decreased the build-up of particles on the stent surface and inside its side-holes. Thus, it demonstrated significant potential for the new side hole configuration to change patterns of crystal deposition on the stent's surface, decreasing encrustation.

#### 2 TRIAL OBJECTIVES AND ENDPOINTS

#### 2.1 PURPOSE OF THE CLINICAL INVESTIGATION

We have identified a reason behind failure of currently used devices and have developed new patented stents preventing blockage by crystals and bacterial build-up. To date, we have conducted laboratory experiments and animal testing, and aim to perform a first in human trial to primarily assess failure rates and determine whether it is suitable to progress the development and testing of the stent further. We will further explore outcomes related to:

- 1. Encrustation and biofilm formation
- 2. Stent lifetime
- 3. Quality of life
- 4. Infection

## 2.2 PRIMARY TRIAL OBJECTIVE AND ENDPOINT

The primary endpoint is stent failure, defined as any of:

- a) a stent change earlier than planned (oncology only);
- b) need for stent related additional surgical or radiological intervention;
- c) kidney failure and/or worsening hydronephrosis.

No intercurrent events (events that would affect the collection or interpretation of stent failure data) are thought likely to occur.

#### 2.3 SECONDARY TRIAL OBJECTIVE AND ENDPOINT

The secondary endpoint is to assess extent of encrustation and biofilm (E&B) via:

- a) Cell culturing (CFU counts per ml per bacterial microorganism)
- b) Dwell time
- c) Imaging (EDIC microscopy, selected samples when needed)

#### 2.4 EXPLORATORY TRIAL OBJECTIVE AND ENDPOINT

The exploratory endpoint is to assess extent of encrustation and biofilm (E&B) via:

- a) Weight: Post-removal, stents will be packaged and sent to the University of Southampton Microbiology Research Laboratory for weighing.
- b) Flow study (pressure value): A section of the retrieved stent will be used for flow study. The part will be placed into a larger diameter tube. DI water/Saline is injected using a pump into the inlet of the external tube and pressure sensor is connected to the inlet tube. Pressure readings will be captured per stent.
- c) Imaging (SEM microscopy, selected samples when needed)

## 2.5 TABLE OF ENDPOINT/OUTCOMES

	Objective	Outcome Measures	Summary method(s)
Primary	To determine rates of stent failure	Stent failure, defined as any of: a) a stent change earlier than planned (oncology only); b) need for stent related additional surgical or radiological intervention; c) kidney failure (evidenced by acute kidney injury (AKI) on blood tests (eGFR or creatinine kidney function tests) and/or worsening hydronephrosis on imaging	Frequency and percentage of people experiencing any stent failure
Secondary	To assess extent of encrustation and biofilm (E&B)	
 
Cell culturing (CFU counts per ml per bacterial microorganism)
 
Dwell time
 
Imaging (selected samples of stents will be examined using non-contact, non-destructive episcopic-differential-interference-contrast (EDIC) microscopy allowing imaging of the surface with the biofilm in-
 
	
 
Mean and standard deviation or median
 
Absolute value (Days)
 

		situ and colonisation by bacteria – when needed).	
	To determine whether the novel stent leads to better clinical outcomes	
 
Individual component of the primary outcome
 
Urinary symptoms
 
Infections
 
	
 
As per primary outcome
 
Frequency and percentage of participants experiencing each symptom
 
Frequency and percentage of people with antibiotic
 
use, readmission, urosepsis, ITU, death; number of infections per
 

	To assess impact of the novel ureteric stent on quality of life	Questionnaires at:      Baseline     While stent is in situ     Post-surgery	unit of time stent is in use Appropriate descriptive summaries (e.g., median and quartiles) per timepoint
	To understand patient experience in having the novel ureteric stent inserted and reason for participation in the trial	30–45-minute Qualitative interviews with Oncology and Kidney stone cohorts	An inductive thematic analysis of interview transcripts
Exploratory	To assess extent of encrustation and biofilm (E&B)	Weight: Stents will be weighed post-removal upon arrival at the microbiology lab	Mean and standard deviation or median and quartiles of weights pre- and post-insertion
		Flow study (pressure value): A section of the retrieved stent will be used for flow study. The part will be placed into a larger diameter tube. DI water/Saline is injected using a pump into the inlet of the external tube and pressure sensor is connected to the inlet tube. Pressure readings will be captured per stent.	Mean and standard deviation or median and quartiles of pressure readings

surface with the biofilm in- situ and colonisation by	
 
Imaging (selected samples of stents will be examined using non-contact, non- destructive SEM (scanning- electron-microscopy)
 
allowing imaging of the
 
	
situ and colonisation by	allowing imaging of the surface with the biofilm in-	
bacteria – when needed).	•	

#### 3 OVERALL TRIAL DESIGN

Two single-arm, multicentre, unblinded, first-in-human trials to investigate a novel ureteric stent in 1) patients with kidney stones and 2) oncology patients. The two separate arms will run simultaneously, with a stopping point to assess the safety of the stent in the Kidney Stone cohort, before the Oncology cohort recruitment commences. This is an early phase trial to assess whether this stent can be inserted and does not have discernible difference in failure or symptoms in patients who have "lived experience" with a previous (market standard) ureteric stent. Each single-arm trial runs in two phases, with a pause to assess safety, and recruitment to the oncology cohort will only occur following safety review for the kidney stone cohort. A qualitative sub study will also be carried out across the two arms. A control group is not included as the aim of the trial is to generate initial first-in-human data to support further development and testing of the novel ureteric stent. Data from a (partly) contemporaneous study (UPPEUS) will be used to support this decision. The design is aligned with the IDEAL framework (designed for novel surgical interventions), and specifically phase 2a of the development process [20]

Kidney stone patients and oncology patients admitted to either the University Hospital Southampton (UHS) or University College London Hospital (UCLH) for management of kidney stones or for the management of urine drainage in ureter will have a novel ureteric stent instead of a conventional stent. The novel ureteric stent will be removed or replaced within 4 weeks (kidney stone patients) or ~25 weeks (oncology patients). Recruitment to the cohort of oncology patients will only commence after a safety review of 10 kidney stone patients have taken place.

The Kidney stone patients will be assessed for safety signals after 10 and 25 patients have had the novel ureteric stents removed (<4 weeks after insertion). Recruitment will continue while the analysis of the first 10 patients takes place. Stopping rules after 10 and 25 patients are summarised in Table 1 below.

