#### 3.1 STOPPING CRITERIA

Table 1 - Stopping rules for kidney stone patients

Criteria	Criteria (1)	Criteria (2)
Event	Rule following 10	Rule following 25
	patients	patients
Insertion (not severe) – clinical judgement: If it is difficult		
to advance because of stent buckling on the side hole,		
then a stiffer wire is used as standard method or stent will		
be changed to		
	Stop/pause and	Stop/pause and
Alternative stent (same make / design but different	investigation if >4 patients	investigation if >10
size French calibre or length) E.g. novel stent 6Fr /	affected	patients affected in total
22cm changed to a novel stent 8Fr 24cm (Not a STOP)		
Different Stent (a different make/design of stent		
regardless of calibre or length) E.g. novel stent 6Fr /		
22cm changed to a Boston 6Fr / 22cm (It is a STOP)		

to reduce the risk. This, if happens, can increase the operation time by approximately 5 mins.		
Removal (could be severe) – clinical judgement: if stent fractures on the side holes, which could increase the chance of needing a surgery (ureteroscopy or even a Percutaneous Nephrolithotomy (PCNL) or a second operation). This is the main reason for pausing the trial until investigation of whether the stent was the cause.	Stop/pause and investigation if >2 patients affected	Stop/pause and investigation if >5 patients affected
Removal of stent <7 days of insertion due to severe infection, overwhelming symptoms, or failure to drain (clinical judgment)	Stop/pause if >4 patients	Stop/pause if >4 patients

If no safety and efficacy concerns are found in the kidney stone patient group (following criteria 1), recruitment of cancer patients admitted to either the University College London Hospital (UCLH) or University Hospital Southampton (UHS) for management of urine drainage in ureter will commence. The cancer patient group will also be assessed for safety signals one week after the 10th patient has had their stent inserted. Another safety assessment of the same cohort will also take place once a further 15 patients have been recruited (25 in total). Recruitment will not be paused during this time.

Table 2 - Stopping rules for cancer patients

Criteria Event	Rule up to the first 10 patients	Rule up to the next 15 patients (ie. 25 in total)
Insertion (not severe) – clinical judgement: If it is difficult to advance because of stent buckling on the side hole, then a stiffer wire is used as standard method or stent will be changed to		

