### 5 SELECTION AND ENROLMENT OF PARTICIPANTS

#### 5.1 PARTICIPANT ENROLMENT

The total expected duration of the clinical investigation will be 16 months. 25 Oncology and 25 Kidney stone patients will be recruited across both sites from UCLH and UHS. Kidney stone patients will be in the study for approximately 4 weeks plus follow-up period, and the Oncology patients will be in the study for approximately 25 weeks plus follow-up period. The recruitment period is 12 months. The inclusion criteria are outlined below. Pregnancy prior to stent insertion is an exclusion criterion, however, any participant that becomes pregnant throughout the duration of the study, will remain in the trial (if they wish) - they will be monitored for any safety related issues and will be followed up until the end of their pregnancy. Only consented patients who are eligible and enrolled into the study will be considered trial participants. Those who do not have the novel ureteric stent inserted will be replaced.

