#### 8.4 INTERIM ANALYSIS

No formal statistical testing at an interim stage is planned. For both the kidney stone and oncology cohorts, there will be an assessment of safety after 10 participants have had the stent removed. There is a safety assessment after the 25 kidney stone patients and up to 15 oncology patients have had the stent removed. See section 3.1 for full details.

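### The insertion row of the stopping rules has no defined denominator or counted event: its labelled stop outcome can never be among the removals that time the kidney stone reviews

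*Protocol*

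**What the plan says.** **Timing, kidney stone cohort.** Section 3: "The Kidney stone patients will be assessed for safety signals after 10 and 25 patients have had the novel ureteric stents removed". Section 8.4, for both cohorts: "there will be an assessment of safety after 10 participants have had the stent removed".

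**Timing, oncology cohort.** Section 3.1 uses other triggers. The first review is "one week after the 10 th patient has had their stent inserted", and the second comes "once a further 15 patients have been recruited (25 in total").

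**The insertion row (Tables 1 and 2).** One event description covers difficulty in advancing the stent. It names three responses: a stiffer wire, another size of the same design (labelled as not a stop), and "Different Stent (a different make/design of stent", whose example in Table 1 reads "22cm changed to a Boston 6Fr / 22cm (It is a STOP"). All sit under the same thresholds: more than 4 patients affected at the 10-patient look, and more than 10 in total at the 25-patient look.

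**Replacement.** Section 5.1: "Those who do not have the novel ureteric stent inserted will be replaced". Section 6.8.2 likewise replaces a patient whose stent is not inserted because of a clinical decision. Section 8.3 is narrower: it replaces only those in whom the insertion procedure is not begun.

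**Recording.** The Safety population in section 8.1 is defined by attempted insertion. Section 7.2.2 records device deficiencies from the moment a device is selected for a participant, even if it is not inserted.

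**The concern.** A patient whose novel stent is exchanged for another make leaves surgery 1 without a novel stent. That patient can never contribute to a count of 10 or 25 removed novel stents, so the trigger for the kidney stone reviews cannot contain the outcome that the row itself marks as a stop. The replacement rules then disagree on whether the patient stays in the cohort at all.

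The numerator is also open. With one threshold over outcomes carrying opposite labels, it is unclear whether a single swap stops the trial, whether five are needed, and whether size changes or use of a stiffer wire add to the count.

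This matters because the 10-patient look in kidney stone patients is the gate for opening oncology recruitment. Section 3 also gives as a trial aim whether the stent can be inserted, and a swap at insertion is not named among the components of the primary endpoint in section 2.2. This row is therefore the only explicit decision rule for that outcome.

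**Working it through.** The protocol gives no operating characteristics for the stopping thresholds, so there is no stated figure to reproduce. It gives no swap rate either; the rates below are assumptions.

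**Inputs.** Threshold at the first look: more than 4, i.e. 5 or more (Table 1). At the second look: more than 10 in total, i.e. 11 or more. Looks at 10 and 25 patients (section 3). Assumed probability *q* that an attempted insertion ends in a change to another make: 20%, 30%, 40%, 50%, independent between patients.

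**Three readings, counting swaps only.**

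(a) Only patients with a removed novel stent are counted. None of them was swapped, so the probability is 0 at every *q*.

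(b) The first 10 (or 25) attempts are counted: P(Bin(10, *q*) ≥ 5) and P(Bin(25, *q*) ≥ 11).

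(c) The review takes place at the 10th (or 25th) removal and every swap up to then is counted. For simplicity, stents are taken to be removed in the order of insertion, and attempts made after the tenth retained stent are ignored. Five or more swaps before the tenth retained stent means five or more swaps in the first 14 attempts: P(Bin(14, *q*) ≥ 5). For the second look it is P(Bin(35, *q*) ≥ 11).

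| Reading | q = 20% | 30% | 40% | 50% |
|---|---|---|---|---|
| First look, (a) | 0 | 0 | 0 | 0 |
| First look, (b) | 3.3% | 15.0% | 36.7% | 62.3% |
| First look, (c) | 13.0% | 41.6% | 72.1% | 91.0% |
| Second look, (a) | 0 | 0 | 0 | 0 |
| Second look, (b) | 0.6% | 9.8% | 41.4% | 78.8% |
| Second look, (c) | 7.5% | 49.0% | 88.8% | 99.2% |

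Expected attempts needed for 10 retained stents, 10/(1 − *q*): 12.5, 14.3, 16.7 and 20.0.

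**Numerator.** Suppose 50% of attempts meet some buckling and 20% end in a swap. Over 10 attempts, P(≥ 5) is 62.3% if any difficulty counts and 3.3% if only swaps count. Among patients who keep a novel stent, the difficulty rate is (0.50 − 0.20)/(1 − 0.20) = 37.5%, and P(Bin(10, 0.375) ≥ 5) = 30.6%. So even on reading (a) the row can be met if difficulty short of a swap is counted; it is the stop-labelled outcome that cannot meet it.

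**Oncology timing.** Section 3.1 places the first review one week after the tenth insertion. Section 8.4 places it after 10 removals, and section 3 puts removal at about 25 weeks. For the tenth patient inserted that is a gap of about 25 − 1 = 24 weeks if the stent stays in as planned. The second reviews also differ: recruitment in section 3.1, removals in section 8.4.

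**The case against.** The strongest reply is that the section 3 sentence fixes when the review happens, not whose data are looked at. A reader might infer that swapped patients are excluded from the review, so that a stent which often cannot be placed would pass the gate unseen. The documents do not support that. No passage limits the review to removed-stent patients, the Safety population is built on attempted insertion, deficiencies are recorded whether or not the stent goes in, and the strict reading would leave the stop label with nothing to count. On reading (c) the rule is more sensitive than a count over 10 attempts. Oncology recruitment also depends on there being no safety or efficacy concerns, which is wider than the row's count, and the DSMC monitors safety under a charter not shown here. The row is itself headed as not severe. For oncology, the second review in section 3.1 is timed by recruitment and Table 2 refers to the first 10 patients; neither leaves swapped patients out.

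It can also be said that the two labels are meant to show which outcome counts towards the threshold. That is plausible, but the row does not say so, and it leaves the stiffer wire unlabelled.

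What stands: intention can be guessed, but the rule cannot be applied in one way from the text. Section 8.3 supports keeping swapped patients in, while sections 5.1 and 6.8.2 replace them. The trigger in sections 3 and 8.4 cannot include the labelled outcome, and sections 3.1 and 8.4 disagree on the oncology triggers.

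**Conclusion.** The point holds as a defect of definition: the insertion row lacks a coherent denominator and a stated counted event, and the passages around it conflict. It should be fixed. It does not show that swapped patients will be overlooked.

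The size depends on assumed swap rates. Across 20% to 50%, the chance that swaps meet the first-look threshold is 0, 3% to 62%, or 13% to 91% on the three readings. At a low swap rate the readings differ little in absolute terms; from about 30% upwards they differ enough to change the decision at the gate. The problem is clearest for the kidney stone reviews. In oncology the main fault is the disagreement between sections 3.1 and 8.4 over timing, together with the shared threshold in Table 2.

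**What to change.** Reconcile sections 3, 3.1 (Tables 1 and 2), 5.1, 6.8.2, 8.1, 8.3 and 8.4. Specifically:

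- State that the insertion row is counted over patients with an attempted insertion (the Safety population), including any who are later replaced.
- State the number of attempts to which each threshold applies.
- State which labelled outcome or outcomes are counted, so that the two opposite labels and the single threshold agree.
- Give one replacement rule for a patient in whom insertion was begun but no novel stent was left in place.
- Give one set of triggers for the oncology reviews in sections 3.1 and 8.4.

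The thresholds, the outcome that counts and the timing of the reviews are for the sponsor and the DSMC; none is proposed here.

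The cost is a protocol amendment and matching wording in the DSMC charter. No new data are needed, because adverse events and device deficiencies at insertion are already recorded. If the sponsor chose to review this row at a different time from the removal rows, that would add review points for the DSMC; counting over attempts at the existing reviews would not.

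### Table 1's second-column stop/pause limits are read only after all 25 planned stone patients have been treated, and no text says what a breach would halt in oncology

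*Protocol*

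**What the plan says.** - **Cohort size.** Section 5.1: "25 Oncology and 25 Kidney stone patients will be recruited across both sites from UCLH and UHS". Section 8.3 gives the same split and allows 3 additional participants for withdrawals, without saying in which cohort.
- **Timing of the stone looks.** Section 3: "The Kidney stone patients will be assessed for safety signals after 10 and 25 patients have had the novel ureteric stents removed". It continues: "Stopping rules after 10 and 25 patients are summarised in Table 1 below". Recruitment is not held for the first look: "Recruitment will continue while the analysis of the first 10 patients takes place".
- **Table 1 (section 3.1).** The two columns are headed as rules *following* 10 and *following* 25 patients. The second-column limits are more than 10 patients (insertion difficulty), more than 5 (fracture at removal) and more than 4 (removal within 7 days). The early-removal entry reads "Stop/pause if >4 patients" in both columns.
- **Link to oncology.** Section 3.1: "If no safety and efficacy concerns are found in the kidney stone patient group (following criteria 1), recruitment of cancer patients" will commence. Section 3 also names the review of 10 stone patients as the condition.
- **Section 8.4.** "There is a safety assessment after the 25 kidney stone patients and up to 15 oncology patients have had the stent removed". It attaches no action to this assessment and refers to section 3.1 for the detail.
- **Table 2 (oncology).** Its columns are worded *up to* the first 10 and *up to* the next 15 patients, 25 in total.

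**The concern.** Section 1.2.5 names the section 3.1 criteria as a risk control, adopted because the device is new. A stop or pause limit does that job only if something remains to be stopped when it is read, or if the text says what else it halts. Criteria (2) meets neither condition as written: the planned stone cohort is complete at that point, and the only written link from stone results to oncology is Criteria (1).

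At stake is a signal that the look at 10 misses and the look at 25 detects. Oncology patients may then be entering, or carrying the same device for about 25 weeks, and the protocol gives the safety committee no stated consequence to apply. The early-removal row shows the gap most clearly. These events are known within 7 days of insertion and the limit does not change between looks, so the printed count can be passed part-way through the cohort while the next stated reading is after 25 removals.

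**Working it through.** The protocol gives no event rate and no operating characteristics for these rules, so there is no figure of its own to reproduce. All rates below are assumptions.

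**1. What is left to stop at the second look.** Planned stone patients 25 (sections 5.1, 8.3); stents removed at the look 25 (sections 3, 8.4). Planned stone insertions left: 25 − 25 = 0. With all 3 extra participants in this cohort: 28 − 25 = 3. Stents still in place among those 25: 0.

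**2. Whether oncology could still be recruiting.** The answer depends on how long stone accrual takes (S months), which is not stated. Assume uniform accrual, 4-week dwell (d = 4/4.345 = 0.92 months), no review lag, and oncology accrual from its release to month 12. Release falls at S × 10/25 + d and the second look at S + d. Oncology patients still to enter = 25 × (12 − second look)/(12 − release), with a minimum of 0.

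| S (months) | Release (month) | Second look (month) | Oncology patients still to enter |
|---|---|---|---|
| 3 | 2.1 | 3.9 | about 20 |
| 6 | 3.3 | 6.9 | about 15 |
| 8 | 4.1 | 8.9 | about 10 |
| 10 | 4.9 | 10.9 | about 4 |
| 12 | 5.7 | 12.9 | 0 |

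A pause in oncology could therefore matter a great deal or not at all. The text does not say whether one would happen.

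**3. How often the early-removal limit would be exceeded between the looks.** Let X10 and X25 be the numbers of early removals among the first 10 and all 25 patients, independent with true rate p. The limit is 5 or more at both looks, so exceeding it at 10 implies exceeding it at 25. Hence

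P(pass at 10, exceed by 25) = P(X25 ≥ 5) − P(X10 ≥ 5), both binomial.

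| p | P(X10 ≥ 5) | P(X25 ≥ 5) | Difference |
|---|---|---|---|
| 5% | 0.0001 | 0.007 | 0.7% |
| 10% | 0.002 | 0.098 | 10% |
| 15% | 0.010 | 0.318 | 31% |
| 20% | 0.033 | 0.579 | 55% |
| 30% | 0.150 | 0.910 | 76% |
| 40% | 0.367 | 0.991 | 62% |

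Among cohorts in the last column, the fifth event falls on average at patient 18.8, 16.7 and 14.7 for p = 20%, 30% and 40%. That leaves about 6, 8 and 10 later stone patients. These counts assume one patient at a time and no reporting lag, so they are upper-end illustrations.

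**4. The other rows.** For fracture (more than 2 at 10, more than 5 at 25), the chance of passing the first look and exceeding the limit by 25 is 0.1% at p = 5%, 1.6% at 10% and 23% at 30%. For insertion difficulty (more than 4, then more than 10) it is 4% at 30%. The gap is mainly in the early-removal row.

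**The case against.** The best answer is that Table 1 is not the only safeguard. Section 1.2.5 sends a participant whose stent fails to drain and who needs further intervention to investigation under the stop/go criteria, whenever that happens. SAEs go to the trials unit within days (sections 7.5.1.3 and 7.6.1). The other site's PI reviews every SAE, and USADEs are reviewed immediately (section 7.6.3). Sections 7.7 and 9.3 give routes to urgent measures and a temporary halt, and section 12.2 sets up a DSMC whose meeting schedule is in a charter not shown here. Many early removals for severe infection or failure to drain would probably count as serious.

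This stands against a stronger reading. A reader might infer that patients 11 to 25 are treated under no rule at all, that nobody checks until patient 25, or that the second column protects no one. The documents do not support that: events are reported and reviewed throughout. What the oversight provisions lack is any tie to the Table 1 counts, or any statement of what a Criteria (2) breach does in oncology.

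A second answer is that the fracture row speaks of pausing the trial, which could mean both cohorts. That is a fair reading for that row. But the phrase appears in no other row of Table 1, its scope is not defined, and section 3 describes two trials.

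A third answer is that the look at 25 still informs whether to develop the stent further, which is a stated purpose of the study. That is correct, but it describes an end-of-cohort review and not a stop or pause rule.

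**Conclusion.** The point holds as a defect in the written rule. Criteria (2) is labelled stop/pause, is read when 0 planned stone insertions remain (at most 3), and has no stated effect on oncology. This follows from the text of sections 3, 3.1, 5.1, 8.3 and 8.4 and needs no assumed rate.

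How often it would matter does depend on assumed rates. For early removal the chance that the limit is passed between the looks runs from 0.7% at a true rate of 5% to 76% at 30%. The 76% is the highest value in the range examined and should not be read as an expected figure, because the protocol gives no rate to choose by. Independence between patients is also assumed.

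Sample size, primary analysis and error rates are unaffected, since section 8.4 plans no formal interim testing. With oversight continuing between looks, this is a should-fix item: a declared safeguard that cannot work as labelled and is cheap to put right.

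**What to change.** Keep the sponsor's counts. Which counts are clinically right is for the sponsor and its safety committee.

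1. Reconcile sections 3, 3.1 and 8.4 on what the second column of Table 1 is. Either it is a cumulative limit applying *up to* 25 patients, as Table 2 is worded, so that it can act while recruitment is open; or it is an end-of-cohort review and should be labelled as one. The sponsor and safety committee should choose.
2. If it is cumulative, say so for every row and say when the count is read. Only the insertion row of Table 1 now says that its limit is a total. A count restarted at patient 11 would loosen the rule: at p = 30% the chance of passing the first look and then triggering falls from 76% to P(X10 ≤ 4) × P(X15 ≥ 5) = 0.850 × 0.485 = 41%. Copying Table 2's heading alone is not enough, because section 3.1 places the second oncology assessment after 25 patients have been recruited.
3. State in section 3.1 which recruitment (remaining stone, oncology or both) a Criteria (2) breach halts and who decides, and define the scope of a trial pause in the fracture row.

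The cost is a table heading and a few sentences in an amendment and, if the limit is cumulative, a running tally at the trials unit. The downside is that a pause could come earlier than now planned.
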